11.5.1 Statistical Analysis of the Primary Efficacy Endpoint

The primary efficacy *parameter is the CFB to Week 6 (or LOCF) in the percentage of catheterizations without a leaking accident. The primary efficacy parameter* will be analyzed using an analysis of covariance (ANCOVA) model with the baseline measure of the primary variable as the covariate and treatment group *and study part (Pre-Amendment 3 and Post-Amendment 3) as factors.*

To assess the effect of the study design, the primary efficacy parameter will be analyzed using a random effects mixed model using the combined data from the Pre-Amendment 3 doubleblind treatment period and the data from the Post-Amendment 3 open-label treatment period. The model will include the baseline measure and other baseline characteristics as covariates and treatment (Pre-Amendment 3 double-blind placebo, Pre-Amendment 3 double-blind oxybutynin chloride gel, Post-Amendment 3 open-label oxybutynin chloride gel) as factors and will account for the heterogeneity between parts of the study (Pre-Amendment 3 vs Post-Amendment 3) by using a random effect for study part. If the analyses indicate heterogeneity, the data from the Pre-Amendment 3 double-blind treatment period and the data from the Post-Amendment 3 open-label treatment period will be analyzed separately. For the Post-Amendment 3 ITT population, the significance of the change from baseline on the primary efficacy measure will be assessed from a 2-sided, 1-sample t-test. For the Pre-Amendment 3 ITT population the primary efficacy parameter will be analyzed using an ANCOVA model with the baseline measure of the primary variable as the covariate and treatment group as factors.

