4.1 Study Design Summary

This study was initiated as a double-blind, placebo-controlled study with an open-label extension and was amended via protocol amendment (Protocol Amendment 3) to enroll participants under only open-label treatment. Therefore, analyses are described with respect to prior to protocol amendment 3 ("pre-amendment 3") and with protocol amendment 3 ("post-amendment 3").

Prior to Amendment 3, participants aged 6 years to < 17 years who had a diagnosis of detrusor overactivity associated with a neurological condition and were using clean intermittent catheterization (CIC) to control bladder function were randomly assigned 1:1 to receive doubleblind oxybutynin chloride gel or placebo gel for 6 weeks. Enrollment was stratified based on sex, age, and weight. Stratification was done within the following groups: male and female; 6 to < 12 years-of-age and 12 to < 17 years-of-age; and by weight category: ≤ 25.0 kg and > 25.0 kg for the 6 to < 12 years-of-age group and \le 50.0 kg and > 50.0 kg for the 12 to < 17 years-of age group. Enrollment into the 6-week treatment period was to be followed by an open-label, 8-week period to generate safety data. All participants began treatment with 0.75 g of gel/day for 2 weeks. Participants then returned to the clinic at Week 2 for a potential dose titration and at this time their dose could have been adjusted up to 1 g/day, down to 0.5 g/day, or remained the same at 0.75 g/day. The determination of dose was based on the investigator's clinical judgment and assessment of the patient's bladder symptoms and treatment side effects. Dose titration was permitted only once during the entire 6-week double-blind, placebo-controlled period. Participants continued blinded treatment for 4 additional weeks until the end of the double-blind treatment period.

Post-Amendment 3, the study became a multicenter, open-label, dose-titration study in pediatric participants, ages 3 years to < 17 years, with detrusor overactivity associated with a neurological condition. A minimum of 25 participants are to be enrolled. Efforts will be made to enroll a greater number of participants from the ages of 3 years to < 6 years. Participants must be suitable

[figure not shown]

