	values at an analysis visit (e.g., Week 6 LOCF)
	 Estimates derived from a model for CFB value controlling for factors (treatment
	group) and covariates (baseline value)
	Least squares (LS) means and standard errors
	LS mean differences, and 95% confidence intervals for oxybutynin chloride
	gel vs Placebo
	 P-values from contrast t-test comparing oxybutynin chloride gel vs Placebo
	N1 = portioinants with non-missing values at both baseline and the specific 1
	• N1 = participants with non-missing values at both baseline and the specified postbaseline analysis visit
Exact (Clopper-	Exact 95% CI for a single proportion
Pearson) 95% CI	Exact 9370 CI for a single proportion
1 carson, 75/0 Cl	

SAP OG09002 Oxybutynin Chloride 10% Gel

Methodology	Description
Exact	• Exact 95% CI for difference between two proportions
unconditional 95%	
CI using the score	
statistic	
Cochran-Mantel-	P-value from CMH test controlling for baseline covariates
Haenszel (CMH)	
Kolmogorov-	P-value from exact Kolmogorov-Smirnov test to examine whether two distributions
Smirnov test	are the same

CFB = change from baseline; ANCOVA = analysis of covariance.

Raw and derived data listings will be provided, and will be fully defined in the table, figure, and data listing specification document.

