5.1.1.3.1 Efficacy Endpoints

The primary efficacy endpoint is the change from baseline (CFB) to Week 6 in the percentage of catheterizations without a leaking accident as recorded in the 2-day urinary diary.

Distributions for the primary endpoint between participants treated with oxybutynin chloride gel in the two different types of treatment periods (Pre-Amendment 3 double-blind treatment period or Post-Amendment 3 open-label treatment period) of the study will be compared. Specifically, an exact two-sample Kolmogorov-Smirnov test will be used to compare the two distributions, with a p-value of 0.05 used as the threshold to reject the null hypothesis that the distributions for the two periods are the same.

If the distributions of the endpoint between these two periods are similar ($p \ge 0.05$), the primary analysis of the primary efficacy endpoint analysis will compare the difference between oxybutynin chloride gel and placebo in the Combined ITT population for the change from baseline in the percentage of catheterizations without a leaking accident at Week 6 using an analysis of covariance (ANCOVA) model with the baseline measure of the primary variable as the covariate and treatment group (active or placebo) as the factor.

If the distributions for the endpoint show a significant difference (p < 0.05) between these two periods, the data from the Pre-Amendment 3 double-blind treatment period and the data from the Post-Amendment 3 open-label treatment period will be analyzed separately as the primary analysis:

• For Pre-Amendment 3, the primary endpoint analysis will compare the difference between oxybutynin chloride gel and placebo in the Pre-Amendment 3 ITT population for the change from baseline in the percentage of catheterizations without a leaking accident at Week 6 using an ANCOVA model with the baseline measure of the primary variable as the covariate and treatment group as the factor.

SAP OG09002 Oxybutynin Chloride 10% Gel

• For Post-Amendment 3, a 2-sided one-sample t-test will be used on the primary endpoint to test for a significant difference from zero in the Post-Amendment 3 ITT population.

The analysis method which is not used as the primary analysis will serve as a supplementary analysis of the primary endpoint.

Secondary endpoints include the change from baseline to Week 6 of treatment in:

- average volume of urine collected per catheterization
- average volume of urine collected at first (morning awakening) catheterization

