Average number of catheterizations per day	Raw value for OC Visits (Week 0, Week 2, Week 6) calculated over 2 diary days	Pre-Amendment 3 Week 0, Week 2, Week 6 of double- blind period; Post-Amendment 3 Week 0, Week 6 of open-label period	Continuous descriptives
Average volume of urine collected per catheterization (for Pre-Amendment 3 population only)	Change from baseline to Week 6 (or LOCF) calculated over 2 diary days	Pre-Amendment 3 Week 6 (LOCF) of double-blind period	CFB ANCOVA Pre- Amendment 3
Average volume of urine collected per catheterization (for Pre-Amendment 3 population only)	Average raw value for Week 6 (or LOCF) calculated over 2 diary days	Pre-Amendment 3 Week 6 (LOCF) of double-blind period	Continuous descriptives
Average volume of urine collected per catheterization (for Pre-Amendment 3 population only)	Change from baseline for OC Visits (Week 2, Week 6) calculated over 2 diary days	Pre-Amendment 3 Week 2, Week 6 of double-blind period	CFB ANCOVA Pre- Amendment 3
Average volume of urine collected per catheterization (for Pre-Amendment 3 population only)	Average raw value for OC Visits (Week 2, Week 6) calculated over 2 diary days	Pre-Amendment 3 Week 0, Week 2, Week 6 of double- blind period	Continuous descriptives
Maximal bladder capacity	Change from baseline to Week 6 (or LOCF)	Pre-Amendment 3 Week 6 (LOCF) of double-blind period; Post-Amendment 3 Week 6 (LOCF) of open-label period; Combined ITT (LOCF)	CFB ANCOVA Pre- Amendment 3; CFB one-sample t-test Post-Amendment 3; CFB ANCOVA for Combined ITT
Detrusor pressure at maximal bladder capacity	Change from baseline to Week 6 (or LOCF)	Pre-Amendment 3 Week 6 (LOCF) of double-blind period; Post-Amendment 3 Week 6 (LOCF) of open-label period; Combined ITT (LOCF)	CFB ANCOVA Pre- Amendment 3; CFB one-sample t-test Post-Amendment 3; CFB ANCOVA for Combined ITT

SAP OG09002 Oxybutynin Chloride 10% Gel

Endpoint	Description	Timing	Methodology
Maximum amplitude of involuntary detrusor pressure	Change from baseline to Week 6 (or LOCF)	Pre-Amendment 3 Week 6 (LOCF) of double-blind period; Post-Amendment 3 Week 6 (LOCF) of open-label period; Combined ITT (LOCF)	CFB ANCOVA Pre- Amendment 3; CFB one-sample t-test Post-Amendment 3; CFB ANCOVA for Combined ITT

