5.2.2 Changes to Analyses Prior to Database Lock

Version	Date	Summary
1.0	24 Oct 2017	Original version
2.0	28 Mar 2022	 Exact (Clopper-Pearson) 95% CI, Exact unconditional 95% CI using the score statistic, and Cochran-Mantel-Haenszel (CMH) was added in Table 5-2 to analyze binary urodynamic variable (Presence (versus total absence) of involuntary detrusor contractions at > 15 cm H2O)
		 CFB Mixed Model was deleted from Table 5-2. All CFB Mixed model analyses have been replaced with CFB ANCOVA as reflected in Table 5-12
		 Study part was removed as a factor from the CFB ANCOVA models
		 Details of how urodynamic assessments will be analyzed have been added in Table 5-12
		 Section 5.1.1.2 was modified to clarify analysis populations presented in demographics tables.
		 Exact Kolmogorov-Smirnov test was added in Table 5-2 to compare whether distributions of efficacy endpoints between patients treated with oxybutynin chloride gel in the two parts (Pre-Amendment 3 and Post-Amendment 3) of the study are the same
		 Section 5.1.1.3.1 was modified to provide details on how efficacy endpoints will be analyzed based on whether the distributions of efficacy endpoints between patients treated with oxybutynin chloride gel in the two parts (Pre- Amendment 3 and Post-Amendment 3) of the study were the same or not
		 Updated Table 5-15 definition of treatment-emergent adverse events in double-blind period to distinguish between participants who enter the 8-week open-label period from those that do not

6. Data Handling and Analysis Conventions

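### For bladder volumes, the Combined ITT ANCOVA omits age although every child under 6 is on gel; this can bias the gel-versus-placebo difference modestly against gel

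*SAP*

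**What the plan says.** SAP Table 5-2 defines the CFB ANCOVA: "Estimates derived from a model for CFB value controlling for factors (treatment" "group) and covariates (baseline value". It contains no other term. SAP 5.1.1.3.1 words the combined model for the primary endpoint in the same way, with "treatment group (active or placebo) as the factor".

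Table 5-12 applies this model, listed as "CFB ANCOVA for Combined ITT", to first-morning volume, maximal bladder capacity and volume at first involuntary detrusor contraction. The Pre-Amendment 3 ANCOVA and the Post-Amendment 3 one-sample t-test are listed beside it.

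Age differs between the groups by design. The randomised part took ages 6 to <17, stratified by age, weight and sex. The open-label part takes ages 3 to <17, all on gel and unstratified (Protocol 9.4.3), and SAP 4.1 adds: "Efforts will be made to enroll a greater number of participants from the ages of 3 years to < 6 years".

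The SAP 5.2.2 entry for version 2.0 records "CFB Mixed Model was deleted from Table 5-2" and "Study part was removed as a factor from the CFB ANCOVA models".

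The Kolmogorov-Smirnov step in SAP 5.1.1.3.1 compares change scores between the two gel groups. It is stated for the primary endpoint and for each secondary endpoint; no such condition is stated for the urodynamic variables. The subgroup analyses in SAP 5.1.1.6 cover primary and secondary efficacy and do not name the urodynamic variables.

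**The concern.** The pooled gel group contains children for whom there is no placebo counterpart of the same age. First-morning volume is recorded in cc or mL (Protocol Appendix 3), and no age-scaled measure is described for any of the three endpoints.

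Adjusting for the baseline value removes only part of an age difference. A child's second reading falls back toward the mean for that child's own age, not toward a mean common to all ages. Of two children with the same baseline, the younger is therefore expected to show the smaller change. With more young children on gel, the adjusted difference picks up age as well as treatment.

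At stake is the size of the gel effect in the combined analysis of two pharmacodynamic variables and, less so, one secondary endpoint.

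**Working it through.** **The plan's own figure.** The only stated power is for the primary endpoint: difference 20, SD 28, 48 per arm. The noncentrality is 20 / (28 × √(2/48)) = 3.50, which gives 93.4% at two-sided 0.05 (assumed), against the stated 93%. With 43 per arm after 10% dropout it is 90.6%, against 90%. Both reproduce. Nothing is stated for the volumes or for the combined analysis.

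**Mechanism.** Let mean volume at a given age be a + b × age, and let r be the test-retest correlation within age. With no gel effect, the expected change given baseline B and age is

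−(1 − r) × (B − a − b × age).

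At fixed baseline, change therefore rises by (1 − r) × b mL per year of age. The bias is that slope times the age gap between arms that remains once baseline is held fixed. It is zero if b = 0 or r = 1. It is negative when gel patients are younger. An effect that is constant in mL is shifted by the same amount.

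**Age gap.** Assume ages uniform within band (means 11.5 and 4.5 years) and half of the open-label children under 6.
- 48 per arm plus 25 open-label: gel mean (48 × 11.5 + 25 × 8.0) / 73 = 10.3 years, a gap of −1.2 years; 17% of the gel group is under 6.
- 15/15/30 (placebo, blinded gel, open-label gel): gel mean (15 × 11.5 + 15 × 4.5 + 15 × 11.5) / 45 = 9.2 years, a gap of −2.3 years.

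With b = 25 and r = 0.5 the slope is 12.5 mL per year. If baseline absorbed none of the gap, the bias would be 12.5 × 1.2 = 15 mL and 12.5 × 2.3 = 29 mL. The simulated values below (−8.2 and −14.1 mL) show that baseline absorbs about half.

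**Simulation, no gel effect and no difference between study parts.** Assumed inputs, none of them in the documents: mean 50 + 25 × age mL, SD 30% of the mean, 15/15/30 patients, 4,000 runs per setting.

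| Open-label share under 6 | r | Bias, planned model (mL) | Bias, age added (mL) |
|---|---|---|---|
| 30% | 0.5 | −10.0 | −1.3 |
| 30% | 0.7 | −5.7 | −0.4 |
| 50% | 0.5 | −14.1 | −0.5 |
| 50% | 0.7 | −8.0 | 0.0 |
| 70% | 0.5 | −17.7 | −0.1 |
| 70% | 0.7 | −9.4 | +1.0 |

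Repeat runs agree to about 1 mL, so I carry forward about −6 to −17 mL for r of 0.5 to 0.7. At r = 0.85 the bias falls to about −2 to −5 mL.

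**Planned sizes.** With 48 per arm plus 25 open-label and half under 6, the same volume model gives −8.2 mL (r = 0.5), −5.2 mL (r = 0.7) and about −2 mL (r = 0.85). With 70% under 6 and r = 0.5 it reaches about −11 mL.

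**Other assumptions.** Take a constant SD of 60 mL, slopes of 10 to 30 mL per year, r of 0.5 or 0.8, 25 open-label patients and 50% to 75% of them under 6. The bias is then −1.6 to −6.6 mL at 48 per arm, −2.1 to −10.0 mL at 24 and −2.6 to −12.8 mL at 10. Adding age brings it within 0.6 mL, with rejection of 4% to 6%.

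**Direction and precision.** At 15/15/30 the estimator's SD is 16 to 29 mL, so the bias is about 0.2 to 0.6 of it. Two-sided rejection under the null is 5% to 14%, nearly all of it showing gel as worse; rejections favouring gel stay at or below the nominal 2.5%. Age costs no precision: with half under 6 and r = 0.5, the standard error goes from 26.6 to 25.0 mL. With SD proportional to the mean, rejection with age added is still about 5% to 9%; with constant SD it is nominal. The remaining excess therefore comes from unequal variance.

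**The case against.** **Size.** The bias is below one standard error in every scenario, and its true size cannot be had from the documents. That volume rises with age in these neurogenic bladders is itself an assumption. All of this stands, and it limits the priority of the point.

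**What is already planned.** The Pre-Amendment 3 ANCOVA is a randomised contrast in ages 6 to <17, stratified by age and weight, and does not have this problem. For first-morning volume, SAP 5.1.1.6 plans age-group analyses for each ITT population. The combined ANCOVA is its main analysis only if the Kolmogorov-Smirnov p-value is at least 0.05. Its baseline also averages two diary days: if a single day had r = 0.5, the average would have about 2 × 0.5 / 1.5 = 0.67. This stands too. It moves the weight of the point to the two urodynamic volumes, which rest on one evaluation at Visit B and have neither safeguard.

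**Readings that go too far.** A reader might infer that the 5% to 14% rejection rate means false claims of efficacy. It does not, because the excess lies on the side where gel looks worse. A reader might also infer that the SAP dropped a documented age adjustment, since Protocol 11.5.1 says "The model will include the baseline measure and other baseline characteristics as covariates". That sentence does not name age and concerns the primary endpoint only. Protocol 11.7.4 plans descriptive summaries alone for urodynamics, and SAP 5.2.2 logs the model changes.

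**Limits of the remedy.** There is no placebo patient under 6, so age adjustment extrapolates there. Open-label gel also remains pooled against blinded placebo. Both stand and should be said with the result.

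**Conclusion.** The point holds in a limited form. For maximal bladder capacity and volume at first involuntary detrusor contraction, and to a lesser degree first-morning volume, the combined model leaves a predictable bias from an age imbalance that the amendment built in.

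Under the assumed slope, variance and reliability it is about −6 to −17 mL at 15/15/30 (r of 0.5 to 0.7) and about −2 to −8 mL at the planned 48 per arm plus 25 open-label with half under 6 (r of 0.5 to 0.85). It vanishes if volume does not depend on age. The likely harm is an understated gel effect in a supportive analysis. The omission does not invalidate the randomised comparison. The change is worth making because it is nearly free, not because the bias is large.

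**What to change.** In SAP Table 5-12, add age in years at screening as a covariate to the Combined ITT CFB ANCOVA for maximal bladder capacity, volume at first involuntary detrusor contraction and first-morning volume. Report the same contrast restricted to ages 6 to <17, also with age in the model. Log both in SAP 5.2.2. Leave the Pre-Amendment 3 ANCOVA and the Post-Amendment 3 t-test as they are.

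State beside the results that the adjustment extrapolates below age 6, does not remove the open-label versus blinded confounding and does not correct unequal variance, so that the Pre-Amendment 3 ANCOVA remains the cleaner contrast.

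The cost is SAP wording, one degree of freedom and one extra contrast per endpoint. Age is already summarised in SAP Table 5-7, so no new data are needed.

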Patients who have completed the washout period and the 2-day urinary diary (*completed by the patient or parent/caregiver*) will have a baseline urodynamic evaluation performed at Visit **B** (Baseline Visit, Week 0 of treatment). **Patients** will be enrolled in the study following the urodynamic measurements. **Patients** will report back to the clinic for scheduled visits at Weeks **2**, **6**, **10**, **and 14** (\pm 2 days) as detailed **below**.

Eligible *patients* will begin treatment *the morning after Visit B (Week 0 of treatment)* with 0.75 g of gel/day. This will be the start of the *14*-week treatment period, and *followed by* 4 additional visits, on Weeks 2, *6*, *10*, and *14* of treatment.

At Visit *C* (Week 2 of treatment), a blood sample will be collected for *PK* analysis. *After study assessments at* Visit *C are completed*, the daily dose may be adjusted up to 1 g/day, down to 0.5 g/day, or remain the same at 0.75 g/day. The determination of dose will be based on the investigator's clinical judgment and assessment of the patient's bladder symptoms and treatment side effects. *Patients* will remain on this dose until the end of the *treatment* period.

A 2-day urinary diary will be completed prior to Visit D, and urodynamic assessments will be performed at Visit D (Week 6 of treatment). A blood sample for PK analysis will also be collected at Visit D.

Safety will be evaluated during the *14*-week *treatment* period by monitoring adverse events *(AEs)*, vital signs, *and* clinical laboratory evaluations, and *by assessing* skin erythema at the most recent application site.

Other evaluations will include a 12-lead electrocardiogram (ECG) at screening and an anticholinergic symptoms questionnaire at *Visits C, D, E, and F*.

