5.1.1.1.4 Missing Data

General missing data handling conventions for methodologies in Section 5.1.1.1.3 are summarized as follows:

Table 5-3 Missing Data Handling by Endpoint Type

Parameter type	Timing	Missing Data Handling
CFB ANCOVA	Treatment Period	 If missing a covariate: ○ Participant excluded If missing derived value at the specified post-baseline analysis visit: ○ Available cases (i.e., observed case [OC] analysis) ■ Participant excluded ○ Last observation carried forward (LOCF) ■ Participant included using LOCF-imputed value (last non-missing post-baseline value before the missing value is carried forward to impute the missing value). Baseline value will not be carried forward.

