Volume at first involuntary detrusor contraction	Change from baseline to Week 6 (or LOCF)	Pre-Amendment 3 Week 6 (LOCF) of double-blind period; Post-Amendment 3 Week 6 (LOCF) of open-label period; Combined ITT (LOCF)	CFB ANCOVA Pre- Amendment 3; CFB one-sample t-test Post-Amendment 3; CFB ANCOVA for Combined ITT
Presence (versus total absence) of involuntary detrusor contractions at > 15 cm H2O	Raw value at Week 6 (or LOCF)	Pre-Amendment 3 Week 6 (LOCF) of double-blind period; Post-Amendment 3 Week 6 (LOCF) of open-label period; Combined ITT (LOCF)	CMH test Pre-Amendment 3; Exact 95% CI Post-Amendment 3; CMH test for Combined ITT

¹ Weeks are defined in Section 6.2.1.

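### SAP Table 5-12 has no rule for patients without contractions, so the non-missing rule removes complete responders from volume at first contraction, and from maximum amplitude if it is left blank

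*SAP*

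**What the plan says.** SAP 5.1.1.3.1, Table 5-12, lists five urodynamic variables. Two of them describe a contraction: "Volume at first involuntary detrusor contraction" and "Maximum amplitude of involuntary detrusor pressure". (Table 5-10 and the protocol give the second as the amplitude of contractions, not pressure.) Each is analysed as change from baseline to Week 6 or LOCF: ANCOVA for Pre-Amendment 3 and for the Combined ITT population, one-sample t-test for Post-Amendment 3.

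The fifth variable is binary: "Presence (versus total absence) of involuntary detrusor contractions at > 15 cm H2O". The plan therefore expects that some tests will show no contraction above that threshold.

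Three rules decide who is analysed:
- **SAP Table 5-2** bases both the ANCOVA and the t-test on "participants with non-missing values at both baseline and the specified" post-baseline visit.
- **SAP Table 5-3** (ANCOVA) lets LOCF use an earlier post-baseline value only: "Baseline value will not be carried forward".
- **Protocol 9.1** says that patients "will have a baseline urodynamic evaluation performed at Visit" B and that "urodynamic assessments will be performed at Visit D (Week 6 of treatment"). The schedules for both study parts show urodynamics only at Week 0 and Week 6. The early-termination visit has none.

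Neither document says what is recorded or analysed when no contraction occurs. Protocol 9.6.2.3, 11.7.4 and Appendix 4 are silent, and so is the SAP. The character-value rule in SAP 6.4.2.3 sits under laboratory data.

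**The concern.** Abolishing involuntary contractions is the best urodynamic result an anticholinergic can give. In that patient there is no first contraction, so no volume at which it occurred. Without a coding rule the value is missing, and the patient leaves the analysis because of the outcome.

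If gel abolishes contractions more often than placebo, more patients leave the gel arm, and those who leave are its best responders. In the Pre-Amendment 3 ITT population this turns a randomised comparison into one between post-randomisation survivors. The Combined ITT comparison, which already mixes randomised and open-label gel patients, inherits the same selection. The Post-Amendment 3 t-test has no comparator to distort, but its mean change would describe only patients who still contract.

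Pharmacodynamics is a stated secondary objective (protocol 8.2), and two of its five variables are exposed. Patients with no contraction at baseline also lack a value, since eligibility requires a diagnosis and not a contraction on the study test. That loss precedes treatment, so it costs numbers but does not by itself unbalance the arms.

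**Working it through.** **1. The plan's own figure.** The only stated power is for the primary diary endpoint: 93% with 48 per arm, 90% after 10% dropout. With difference 20, SD 28 and two-sided alpha 0.05 (implied by the 95% intervals), the noncentrality is 20 / (28 × √(2/48)) = 3.50. The noncentral t gives 93.4%. At 48 × 0.9 ≈ 43 per arm it gives 90.6%. Both reproduce, but they say nothing about the urodynamic variables, for which no figure is stated. Everything below uses assumed inputs.

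**2. A patient with contractions at Week 0 and none at Week 6.**

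| Variable | Week 6 value | Result under Tables 5-2 and 5-3 |
|---|---|---|
| Volume at first contraction | none exists | excluded; no earlier post-baseline test to carry |
| Maximum amplitude | 0 if entered, else blank | kept if 0, excluded if blank |
| Presence above 15 cm H2O | absent | kept |

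**3. Numbers remaining.** Assume 5-10% abolished on placebo and 15-40% on gel. The planned 48 per arm becomes 48 × 0.95 = 45.6 down to 48 × 0.90 = 43.2 on placebo, and 48 × 0.85 = 40.8 down to 48 × 0.60 = 28.8 on gel. The 25 open-label patients become 25 × 0.85 = 21.2 down to 25 × 0.60 = 15.0. These are planned sizes; the documents do not give the number actually randomised.

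**4. Amplitude, if left blank.** Assume baseline mean 40 cm H2O, and change among those still contracting of −10 on gel and 0 on placebo. Dropping gives −10. With abolished cases coded 0, the difference is [(1 − pG)(−10) + pG(−40)] − [pP(−40)].

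| Abolished, placebo / gel | Coded 0 | Share kept by dropping |
|---|---|---|
| 5% / 15% | −14.5 + 2 = −12.5 | 0.80 |
| 5% / 25% | −17.5 + 2 = −15.5 | 0.65 |
| 10% / 30% | −19 + 4 = −15.0 | 0.67 |
| 10% / 40% | −22 + 4 = −18.0 | 0.56 |

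The loss is 20-44%. If treatment lowers amplitude only in proportion, it is about 3% (0.97 kept).

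**5. Volume, same effect in everyone.** Simulation of 400,000 per arm. Each patient has a latent contraction volume (mean 110 mL, SD 45, correlation 0.5 between visits), and a contraction is seen only if that volume is below capacity (mean 200 mL, SD 40). Patients have a contraction at baseline; gel adds a fixed shift. Entries are differences in mean change (mL).

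| Shift | Abolished, placebo / gel | Latent | Dropped | Coded at capacity | Dropped ÷ latent |
|---|---|---|---|---|---|
| 20 | 4.1% / 8.6% | 19.8 | 17.9 | 18.6 | 0.90 |
| 40 | 4.1% / 16.0% | 39.8 | 35.4 | 36.3 | 0.89 |
| 60 | 4.1% / 26.8% | 59.9 | 52.3 | 52.0 | 0.87 |
| 80 | 4.1% / 39.6% | 79.5 | 68.4 | 65.1 | 0.86 |

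The loss here is 10-14%. Other uniform-effect settings kept 0.92-0.99. Adjusting for baseline makes the loss a few points larger on the inputs in the table, so the range is indicative and not a bound.

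**6. Volume, mixed response.** If 30% of gel patients shift by 80 mL and the rest by nothing, the true average effect is 0.30 × 80 = 24 mL. Dropping kept 0.63 of it, about 15 mL. When responders' capacity also rose by 40 mL, fewer were abolished and dropping kept 0.87, about 21 mL. Against capacity coding, with 30-40% responders, dropping kept 92% for a 60 mL shift, 76-79% for 100 mL and 54-57% for 140 mL. Across a wider set of mixed-response inputs, dropping kept 36-86% of the latent effect and capacity coding 66-94%.

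**The case against.** - **Exclusion is inferred.** A reader might take the SAP to order the best responders out of both variables. It does not: exclusion follows from a non-missing rule together with the absence of a derivation rule. Table, listing and dataset specifications are separate documents not seen here. This stands. It does not rescue volume, where any number entered would be an imputation that the SAP does not describe.
- **Amplitude has a natural value.** No contraction means an amplitude of 0, and a site may record it so. This stands, and it is why amplitude is affected only if blank. Handling would then depend on how each site completes the form.
- **The binary variable proves less than it seems.** It uses a threshold of 15 cm H2O. A patient with small contractions can count as absent there and still have both measurements, so it does not show how many values would be lost. This stands. It also keeps abolished cases, but it cannot repair the two continuous estimates.
- **The larger figures come from chosen inputs.** Nothing in the documents favours mixed response over a uniform effect, and a rise in capacity shrinks the loss. This stands.
- **Capacity coding is not clearly better.** In step 5 it is further from the truth than dropping at the two largest shifts. This stands as a reason not to rely on it alone.
- **Consequences are limited.** Protocol 11.7.4 plans only descriptive summaries, and the reported numbers analysed would show unequal loss. The SAP does add tests, however, and a count alone would not separate absent contractions from tests not done.

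**Conclusion.** The gap is real and should be closed. As written, the plan removes from volume at first contraction any patient whose contractions are abolished, and LOCF cannot restore them. Maximum amplitude is affected only where the field is blank. The gel-placebo ANCOVA then selects on a treatment-affected outcome, and the Post-Amendment 3 t-test describes only patients who still contract.

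The size cannot be derived from the documents. Under assumed inputs the loss of effect is about 1-14% for volume with a uniform effect, and about 10-65% with mixed response or outright abolition. The result rests on the unknown share abolished in each arm, on how response is spread across patients, on whether capacity rises, and on how sites record absence.

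A reader might go further and infer that the urodynamic effects are known to be heavily biased, that a false benefit could arise, or that the efficacy conclusion is in doubt. The documents support none of these. In every setting above the difference shrank toward no effect. The primary and secondary endpoints come from the diary and are untouched.

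**What to change.** Before database lock, amend SAP 5.1.1.3 and Table 5-12:

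1. Separate no contraction observed from test not done, using source records where the form does not distinguish them.
2. Set maximum amplitude to 0 when no contraction is observed, and align the variable's name across Table 5-10, Table 5-12 and the protocol.
3. Treat volume at first contraction as right-censored at that test's maximal bladder capacity, at baseline as well as Week 6. Use censored regression, or a rank analysis with absence as the best outcome, and state how a patient without contractions at both visits is ranked. Show simple capacity substitution and the observed-only analysis as sensitivity analyses.
4. Report the number without contractions by arm and visit.

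The cost is SAP wording, two derivation rules and some programming. Appendix 4 of the protocol already collects maximal capacity, so no new measurement is needed. The downside is that capacity substitution understates the gain in volume and can do slightly worse than dropping when the effect is uniform, so it should not be the only analysis. Censored regression adds a distributional assumption, which the rank analysis avoids.
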